11.3 Adverse Events of Special Interest (AESIs)

Treatment-emergent AESIs, including important identified risks and potential risks, will be identified by the search criteria provided in [Table 3](#).

Table 3. Adverse Events of Special Interest

Adverse Events of Special Interest	MedDRA Search Criteria/Codes
important identified risks	
Pleural Effusion	PTs: 10035598 Pleural Effusion 10003522 Aspiration Pleural Cavity 10063045 Effusion
Pericardial Effusion	PTs: 10034474 Pericardial Effusion 10007610 Cardiac Tamponade 10034471 Pericardial Drainage 10063045 Effusion
Generalized Edema	PT 10018092 Generalised Oedema
Photosensitivity Reaction	PT 10034972 Photosensitivity Reaction
Important Potential Risks	
Pneumonitis	PTs: 10035742 Pneumonitis 10035745 Pneumonitis Chemical 10037765 Radiation Pneumonitis 10066728 Acute Interstitial Pneumonitis 10022611 Interstitial Lung Disease

Table 3. Adverse Events of Special Interest (Continued)

Adverse Events of Special Interest	MedDRA Search Criteria/Codes
important identified risks	
Pleural Effusion	PTs: 10035598 Pleural Effusion 10003522 Aspiration Pleural Cavity 10063045 Effusion
Pericardial Effusion	PTs: 10034474 Pericardial Effusion 10007610 Cardiac Tamponade 10034471 Pericardial Drainage 10063045 Effusion
Generalized Edema	PT 10018092 Generalised Oedema
Photosensitivity Reaction	PT 10034972 Photosensitivity Reaction
Important Potential Risks	
Pneumonitis	PTs: 10035742 Pneumonitis 10035745 Pneumonitis Chemical 10037765 Radiation Pneumonitis 10066728 Acute Interstitial Pneumonitis 10022611 Interstitial Lung Disease
Other AESIs	
Anemia	SMQ 20000029: Haematopoietic Erythropenia (broad)
Neutropenia	SMQ 20000030: Haematopoietic Leukopenia (broad)
Infusion-Related Reaction	10051792 Infusion related reaction
Thrombocytopenia	SMQ 20000031 Haematopoietic Thrombocytopenia (broad)
Haemorrhages	SMQ 20000039 Haemorrhage Terms (Excluding Laboratory Terms; narrow)
Hypoalbuminemia	PTs: 10020942 Hypoalbuminaemia 10005287 Blood Albumin Decreased 10005286 Blood Albumin Abnormal

Table 3. Adverse Events of Special Interest (Continued)

Adverse Events of Special Interest	MedDRA Search Criteria/Codes
Other AESIs	
Cutaneous Reaction	SOC 10040785 Skin and Subcutaneous Tissue Disorders The observed TEAEs under this SOC will be medically adjudicated to maintain a list of PTs that are not medically relevant and that will be excluded from the analysis. Current list of PTs to exclude: 10001760 Alopecia 10002424 Angioedema 10011985 Decubitus Ulcer 10014080 Ecchymosis 10020642 Hyperhidrosis 10051235 Madarosis 10070533 Nail Bed Disorder 10028694 Nail Disorder 10062283 Nail Ridging 10028692 Nail Discolouration 10029410 Night Sweats 10034754 Petechiae 10037087 Pruritus 10052576 Pruritus generalised 10037549 Purpura 10042682 Swelling Face
Edema	PTs: 10030095 Oedema 10030124 Oedema Peripheral 10048961 Localised Oedema 10018092 Generalised Oedema 10042674 Swelling 10016807 Fluid Retention 10016803 Fluid Overload 10024770 Local Swelling 10048959 Peripheral Swelling 10007196 Capillary Leak Syndrome 10015993 Eyelid Oedema 10016029 Face Oedema 10052139 Eye Oedema 10034545 Periorbital Oedema
Hepatotoxicity	SMQs: 20000007 Drug-Related Hepatic Disorders (severe events only; broad) 20000009 Cholestasis and Jaundice of Hepatic Origin (broad) 20000008 Liver Related Investigations, Signs and Symptoms (broad) Exclude PT 10020942 Hypoalbuminaemia from this search since hypoalbuminemia is associated with chronic liver disease and therefore not included in AESI

Time to onset

Time to onset is the Rx Day of the start date of the first occurrence of AESI. If a subject has not experienced an AESI, the subject will be censored on the day of the subject's last assessment (i.e., the day of the subject's last known laboratory assessment, last known vital sign assessment, last known physical exam, last known tumor assessment, or last known follow-up visit, whichever is the latest) or 70 days from the last study drug administered, whichever is earliest; if the subject has not experienced an AESI and had no post-baseline assessment (i.e., none of laboratory assessment, vital sign assessment, physical exam, or tumor assessment), the subject will be censored on the day of the subject's first study drug.

Median onset time will be estimated using a Kaplan-Meier method with corresponding 95% CI for the median for each treatment arm.

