Among subjects with SCLC treated with rovalpituzumab tesirine 0.3 mg/kg q6w, 96.8% of subjects reported at least 1 adverse event. The most frequently reported adverse events among subjects with SCLC treated with rovalpituzumab tesirine 0.3 mg/kg q6w were decreased appetite (28.0%), photosensitivity reaction (27.7%), oedema peripheral (27.2%), dyspnoea (26.6%), and nausea (25.6%). Important identified risks following treatment with rovalpituzumab tesirine include: pleural effusions (33.9%), pericardial effusions (16.7%), generalized edema (2.7%) and photosensitivity reactions (27.7%). Important potential risks following treatment with rovalpituzumab tesirine include pneumonitis (1%). The following adverse events of special interest have also been identified: cutaneous reactions (48.7%), thrombocytopenia and hemorrhage events (28%), edema (33.8%), hypoalbuminemia (16.2%), hepatotoxicity (19.3%), nephrotoxicity (5.9%), anemia (19.7%), neutropenia (9.2%) and infusion related reaction (0.2%). In addition, preclinical toxicology studies conducted in the rat and the cynomolgus monkey have identified bone marrow, lung, and kidney as potential sources of clinical adverse events (AEs) (AbbVie Investigator Brochure v7). Accordingly, safety assessments will include regular assessments at protocol-specified time points of routine physical examination, laboratory and imaging tests including CT/MRI assessments and echocardiograms, a fluid retention questionnaire, and daily weights (Section 5.3.1.1). The timing and frequency of these assessments are designed so that potential rovalpituzumab tesirine-related toxicities are identified prior to additional drug doses, limiting the risk of toxicity exacerbation. The dose delay/reduction/discontinuation protocol guidelines provide additional level of risk mitigation for subjects enrolled in this study.

It is thus considered that the study has acceptable benefit/risk profile for subjects with ED SCLC and stable disease or better following completion of four cycles of platinum-based standard front line treatment, taking into account short progression-free and overall survival of these subjects.

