#### 5.5.4.2.2 Dose Reduction Guidelines

Blinded investigational product dose reductions and discontinuation of blinded investigational product for specific toxicities should occur as outlined in Table 4, Dose Reductions for Blinded Investigational Product (IP) and Table 5, Dose Reductions and Discontinuation for Unacceptable Toxicities. Dose reductions for unacceptable toxicities described in Table 5 are mandatory. Reduced dose levels are described in (Table 4). Generally, if unacceptable toxicity recurs after two dose reductions, treatment will be discontinued (for further details, refer to Table 5). If the blinded investigational product dose is reduced, no re-escalation will be allowed. If different unacceptable toxicities occur in sequential treatment cycles (e.g., Grade 3 LFT after the first dose and Grade 3 thrombocytopenia lasting more than 7 days after the second dose), dose reduction will proceed to the next lower dose level. If different unacceptable toxicities occur within one cycle, maximum specified dose reduction will be implemented. Dose reductions and discontinuation are not planned for dexamethasone/placebo. If full dose of dexamethasone/placebo cannot be administered due to an AE, the blinded infusion should be delayed until dexamethasone/placebo can be administered.

Exceptions to the dose modification guidelines should be discussed with the TA MD prior to implementation.

Details of toxicity management are further outlined in Section 6.1.8, Toxicity Management.

Table 4. Dose Reductions for Blinded Investigational Product (IP)

Starting Dose	First Dose Reduction (Reduce Dose)	Second Dose Reduction (Reduce Dose)
0.3 mg/kg	0.2 mg/kg	0.1 mg/kg

[figure not shown]

Table 5. Dose Reductions and Discontinuation for Unacceptable Toxicities

Toxicity a	First Occurrence	Second Occurrence
Grade 3 thrombocytopenia lasting more than 7 days	Reduce dose to 0.2 mg/kg	Reduce dose to 0.1 mg/kg
Grade 4 thrombocytopenia/Grade 3 thrombocytopenia with bleeding/Need for platelet transfusion	Reduce dose to 0.1.mg/kg	Discontinue Blinded IP
Grade 4 neutropenia lasting more than 7 days	Reduce dose to 0.2 mg/kg	Reduce dose to 0.1 mg/kg
Grade 3 febrile neutropenia	Reduce dose to 0.2 mg/kg	Reduce dose to 0.1 mg/kg
Grade 4 febrile neutropenia	Reduce dose to 0.1.mg/kg	Discontinue Blinded IP
Grade 3 Liver Function Tests (LFTs)	Reduce dose to 0.2 mg/kg	Reduce dose to 0.1 mg/kg

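### The SAP identifies the AESI labelled 'Neutropenia' solely by a broad leukopenia search, so captured adverse events in other white cells would be reported under that label

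*SAP*

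**What the plan says.** SAP Section 11.3 states that treatment-emergent AESIs "will be identified by the search criteria provided in" Table 3, so that table alone decides what counts as each AESI. The row labelled 'Neutropenia' holds one entry, "SMQ 20000030: Haematopoietic Leukopenia (broad" scope).

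The two neighbouring blood-count rows are built the same way. Anemia uses "SMQ 20000029: Haematopoietic Erythropenia (broad" scope) and thrombocytopenia uses "SMQ 20000031 Haematopoietic Thrombocytopenia (broad" scope).

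Elsewhere Table 3 trims searches that reach wider than the AESI. For cutaneous reaction, events under the system organ class "will be medically adjudicated to maintain a list of PTs that are not medically relevant", and a list of excluded terms is given. For hepatotoxicity the instruction is: "Exclude PT 10020942 Hypoalbuminaemia from this search".

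The protocol uses the neutrophil label throughout. Section 3.5 reports programme AESI rates that include "anemia (19.7%), neutropenia (9.2%) and infusion related reaction (0.2" percent). Section 5.5.4.1 sets a dosing-day criterion on absolute neutrophil count. Table 5 has rows for "Grade 4 neutropenia lasting more than 7 days" and for febrile neutropenia. Appendix H grades a decreased neutrophil count on neutrophils alone.

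**The concern.** Neutrophils are one white-cell type among several, and the SAP's own laboratory list (Table 4) treats total white cells, neutrophils, lymphocytes and monocytes as separate parameters. A search whose title covers low white cells in general measures a wider quantity than the label 'Neutropenia' promises.

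Two planned results carry that label. One is the AESI incidence, reported as counts and percentages under the general rule in SAP Section 11.1. The other is the Kaplan-Meier time to onset in Section 11.3, which takes the first occurrence of the AESI. A clinical reader would take both as statements about neutrophils, and neither document says that the category is meant to include other forms of leukopenia.

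**Working it through.** The plan states no figure that this point could reproduce, so the check is a reading of the rows and of what follows from them.

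**1. Label against search, for the three blood-count AESIs in Table 3.**

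| AESI label | Search named | Same cell line? |
|---|---|---|
| Anemia | Erythropenia, broad | Yes, red cells |
| Thrombocytopenia | Thrombocytopenia, broad | Yes, platelets |
| Neutropenia | Leukopenia, broad | No: all white cells against one type |

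**2. Is the search narrowed anywhere?** Cutaneous reaction has adjudication and an exclusion list, hepatotoxicity drops a term, and haemorrhages is limited to narrow scope. The neutropenia row has no such step, and nothing in SAP Sections 11.1 to 11.5 adds one.

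**3. What the row would count.** Let S be the subjects with any captured term and N the subjects with a neutrophil term. Assume that the search includes the neutrophil terms; the documents do not list its content. Then:

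- reported 'neutropenia' = S = N + (subjects with a captured white-cell term but no neutrophil term);
- a subject's onset day = the earliest captured term, which is the same as or earlier than the earliest neutrophil term.

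Under that assumption the direction is known: the subject count can only be equal or higher, and an individual onset day can only be equal or earlier.

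**4. Which events can enter.** The search runs on coded adverse events, not on laboratory counts. Protocol Section 6.1.1.1 makes a laboratory abnormality an adverse event only if it leads to discontinuation from the study, needs medical intervention, meets protocol-specific criteria or is judged an adverse event by the investigator. An unreported fall in lymphocytes does not reach Table 3.

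**5. Size.** The second term in step 3 needs event counts by preferred term, which neither document contains. The 9.2% in Protocol Section 3.5 does not help, because its search is not stated. If it came from this broad search, it already includes any other captured leukopenia terms. If it came from a neutrophil-only search, it does not. No over-count can be calculated either way.

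**The case against.** The strongest reply is that this is a naming question about a deliberately sensitive search. All three blood-count rows use a broad haematopoietic search. Over-detection is the safer error when screening for harm, and a neutrophil-only list could miss a case that a site reported only as low white cells. Both arms use the same search, and Section 11.1 excludes between-arm comparisons and p-values.

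Neutrophil-specific results are also planned elsewhere. Section 11.2 tabulates every treatment-emergent event by preferred term and maximum grade, Section 11.4 lists events of Grade 3 or higher, and Section 11.5 gives CTCAE grade shifts, with neutrophils as their own parameter.

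Most of this stands, and it keeps the point minor. It does not correct the two lines headed 'Neutropenia', and no neutrophil-specific time to onset is planned anywhere. The SAP does not say that breadth was chosen for sensitivity. If it was, keeping the broad search under an accurate label preserves it.

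Two stronger readings are tempting, and the documents support neither.

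- A reader might infer an artificial difference between arms, on the view that dexamethasone accompanies active treatment and shifts other white cells. The readable text speaks of dexamethasone or placebo without saying outright which arm gets the active steroid. Nothing in either document describes a steroid effect on white cells, or says that such changes would be reported as adverse events.
- A reader might take 9.2% as the true neutropenia rate and add an assumed surplus to project an inflated figure. The surplus would be invented and the search behind the base is unknown, so the surplus might be counted twice.

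**Conclusion.** The label and the search do not match. Followed as written, any captured adverse event in total or non-neutrophil white cells would enter the 'Neutropenia' AESI incidence and could set its onset date.

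This rests on the search's title; its term content is not in the documents, so which non-neutrophil terms enter cannot be shown from them. The size of the over-count is unknown and could be small. The effect is confined to the AESI summary and its time to onset. No efficacy analysis or type I error is affected. The neutrophil-count dosing criterion and the Table 5 rows do not use this search, so no dosing rule changes either. Severity: minor.

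**What to change.** Make the change before unblinding, the point by which SAP Section 3.0 says the plan will be final, so that it cannot look data-driven.

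- Keep the existing broad-search row in Table 3 and relabel it 'Leukopenia' or 'Neutropenia/leukopenia'.
- Add a 'Neutropenia' row defined by a medically reviewed list of neutrophil-specific preferred terms in the MedDRA version used for coding. The protocol's own terms (neutropenia, febrile neutropenia, decreased neutrophil count) are a starting point.
- Report incidence and time to onset for both rows.

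The cost is one table row, one review of a short term list and one more output line. No sensitivity is lost, because the broad search stays. The new neutropenia row may not match earlier programme reports; a footnote stating the search used for each row would let readers see why.

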# 6.1.8.1 Management of Serosal Effusions/Serositis

Serosal effusions (pleural or pericardial, or ascites) have been observed with rovalpituzumab tesirine and have the potential to be life-threatening (e.g., cardiac tamponade). Therefore, development of any of these events or worsening from baseline warrants prompt evaluation by the Investigator or designee. Alternative causes such as infection, congestive heart failure, or disease progression, should be ruled out. When appropriate, a unifying diagnosis should be reported, e.g., "heart failure," not the signs and symptoms "pleural effusion" and "edema limbs." Effusion events were reported during treatment and may occur up to several months after last Rova-T dose. As a result, subjects should be advised of signs and symptoms of fluid retention and contact treating physician if they arise during this time.

When considered clinically significant (e.g., Grade 2 or higher and considered related to blinded investigational product):

- Systemic corticosteroids, when initiated promptly, have been reported to be beneficial in some prior cases. The Investigator should consider a tapering regimen, such as dexamethasone up to 8 mg orally twice a day for 5 days, followed by 4 mg orally twice a day for 5 days, then 2 mg orally twice a day for 5 days. Alternatively, nonsteroidal therapies for serositis may be considered, such as non-steroidal anti-inflammatory drugs (NSAIDs, e.g., ibuprofen 400 600 mg orally three to four times daily) or colchicine (e.g., 0.6 mg orally two to three times daily) given for 1 2 weeks.
- Until clinical experience suggests otherwise, guidance for dose delay and/or reduction, as well as criteria for ongoing dosing, should follow Section 5.5.4.2.

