## Abyle Rovalpituzumab Tesirine M16-298 Protocol Amendment 4 EudraCT 2016-003503-64

Group	Adverse Event	Grade 1	Grade 2	Grade 3	Grade 4
Serosal Effusions (cont.)	Definition: A disorder chara demonstrate a state of genera medications, or poisoning. I	cterized by leakage of intrav Ilized leaky capillaries follow t can lead to generalized eder	Definition: A disorder characterized by leakage of intravascular fluids into the extravascular space. This syndrome is observed in patients who demonstrate a state of generalized leaky capillaries following shock syndromes, low-flow states, ischemia-reperfusion injuries, toxemias, medications, or poisoning. It can lead to generalized edema and multiple organ failure.	alar space. This syndrome is states, ischemia-reperfusion	
Edema	Edema face	Localized facial edema	Moderate localized facial edema; limiting instrumental ADL	Severe swelling; limiting self-care ADL	1
	Definition: A disorder chara	cterized by swelling due to e	Definition: A disorder characterized by swelling due to excessive fluid accumulation in facial tissues.	acial tissues.	
	Edema limbs	5 – 10% inter-limb discrepancy in volume or circumference at point of greatest visible difference; swelling or obscuration of anatomic architecture on close inspection	> 10 – 30% inter-limb discrepancy in volume or circumference at point of greatest visible difference; readily apparent obscuration of anatomic architecture; obliteration of skin folds; readily apparent deviation from normal anatomic contour; limiting instrumental ADL	> 30% inter-limb discrepancy in volume; gross deviation from normal anatomic contour; limiting self- care ADL	1-
	Definition: A disorder chara	cterized by swelling due to e	Definition: A disorder characterized by swelling due to excessive fluid accumulation in the upper or lower extremities.	he upper or lower extremities	
	Edema trunk	Swelling or obscuration of anatomic architecture on close inspection	Readily apparent obscuration of anatomic architecture; obliteration of skin folds; readily apparent deviation from normal anatomic contour; limiting instrumental ADL	Gross deviation from normal anatomic contour; limiting self- care ADL	1
	Definition: A disorder chara	cterized by swelling due to e	Definition: A disorder characterized by swelling due to excessive fluid accumulation in the trunk area.	he trunk area.	

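### SAP Table 3 leaves the preferred term Swelling Face in no adverse-event-of-special-interest search, and has no ascites term and no row for any serosal effusion

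*SAP*

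**What the plan says.** SAP Section 11.3, Table 3, gives the search for each AESI.

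- **Pleural Effusion**, an important identified risk: "10035598 Pleural Effusion 10003522 Aspiration Pleural Cavity 10063045 Effusion".
- **Pericardial Effusion**, an important identified risk: "10034474 Pericardial Effusion 10007610 Cardiac Tamponade 10034471 Pericardial Drainage 10063045 Effusion".
- **Generalized Edema**, an important identified risk: "PT 10018092 Generalised Oedema".
- **Edema**, listed among the other AESIs: 14 preferred terms. They include Swelling, Local Swelling, Peripheral Swelling, Face Oedema, Eyelid Oedema, Eye Oedema and Periorbital Oedema.
- **Cutaneous Reaction**, also among the other AESIs: the skin system organ class less a current list of excluded terms, which ends with "10037549 Purpura 10042682 Swelling Face".

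The same section defines time to onset, for AESIs only.

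The protocol groups fluid-retention toxicity differently. Section 6.1.8.1 opens with "Serosal effusions (pleural or pericardial, or ascites) have been observed with rovalpituzumab tesirine". Appendix H places ascites in its Serosal Effusions group and grades facial edema in its Edema group, with Grade 1 given as "Localized facial edema". Table 5 in Section 5.5.4.2.2 has rows for serosal effusions or edema by grade, and its footnote refers to Appendix H for what those words cover.

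**The concern.** Fluid retention is a central toxicity of this drug. The AESI rows are where the report will group it, and the only place where time to onset is planned. A term outside every search adds to no grouped rate and has no onset curve. A toxicity group that the protocol uses for grading and dose rules, but that has no row in Table 3, cannot be read off the report as a number of subjects.

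Both problems appear in Table 3. Swelling Face is removed from one search and not taken up by the search where its neighbours sit. Ascites belongs to the protocol's serosal-effusion group but is in no listed term, and the group itself has no row.

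**Working it through.** The plan gives no figure to reproduce here. The check is one of set membership on the MedDRA codes printed in Table 3, followed by what the other planned tables can and cannot supply.

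**1. Swelling Face (10042682).** It is on the Cutaneous Reaction exclusion list and is not among the 14 Edema codes. It is not in the pleural, pericardial, generalized edema, photosensitivity, pneumonitis, infusion-reaction or hypoalbuminemia lists either. Face Oedema (10016029) is in Edema. So two neighbouring terms for a swollen face are treated differently: one counts as edema, the other counts in no listed AESI.

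**2. Ascites.** None of the preferred terms printed in Table 3 is ascites. The table also uses standardised queries, for example for hepatotoxicity. Their contents are not in the documents, so whether one of them picks up ascites cannot be checked. They are not fluid-retention searches in any case. Of the other Appendix H serosal terms, tamponade is covered by the pericardial search and capillary leak syndrome by the Edema search, so ascites is the one left out.

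**3. Overlap.** The pleural and pericardial searches share exactly one code, 10063045 (Effusion). Generalized Edema and Edema share 10018092. No other pair of listed-term searches overlaps.

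**4. Can the other tables fill the gap?** SAP Section 11.2 counts each subject once per preferred term, once per system organ class and once overall. Ascites and Swelling Face will therefore appear as single lines. The number of subjects with any serosal effusion will not. If the rates of two terms are a and b in the same subjects, the rate of either lies between max(a, b) and a + b (when that is below 100%). Protocol Section 3.5 reports 33.9% pleural and 16.7% pericardial effusion. On the assumption that both share one denominator:

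- lower bound: max(33.9, 16.7) = 33.9%
- upper bound: 33.9 + 16.7 = 50.6%

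The marginal rates leave a range of 50.6 − 33.9 = 16.7 percentage points, before ascites is considered. These are programme figures, used only to show that separate rows do not give a combined count. The documents do not say that the Table 3 searches produced them.

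**5. Possible size per subject.** Assume 740 subjects randomized 1:1 and all treated, so 740 / 2 = 370 per arm. If k subjects in an arm have the term in question and no other term of that search, the rate moves by 100 × k / 370 percentage points.

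| k per arm | change (percentage points) |
|---|---|
| 0 | 0 |
| 1 | 0.27 |
| 2 | 0.54 |
| 5 | 1.35 |
| 10 | 2.70 |

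For Swelling Face this is the amount by which the Edema row would be too low. For unspecified Effusion it is the most that could be added to whichever site-specific row is not the true site. The documents give no value of k for either term.

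**The case against.** The strongest reply is that nothing is hidden. Every treatment-emergent event is tabulated by system organ class, preferred term and maximum grade. Events leading to dose reduction, discontinuation or death are summarized, and serious and Grade 3 or higher events are listed (SAP Sections 11.2 and 11.4). Safety analyses make no comparison between arms (Section 11.1). Appendix H serves grading and dose rules, and no document requires an AESI of the same make-up. All of this stands, and it keeps the point small. It does not supply the two things lost: a subject-level count of any serosal effusion or any edema, and an onset analysis for the missing terms.

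Five stronger readings are tempting, and the documents do not support them.

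- **That the main identified risks are miscounted.** The four in Protocol Section 3.5 and in Table 3 are pleural effusion, pericardial effusion, generalized edema and photosensitivity. Ascites and Swelling Face are not among them, and the wider Edema search is under other AESIs.
- **That facial swelling as such is left out.** Face Oedema and three periocular terms are in the Edema search. Only the single term Swelling Face is missing.
- **That placing Effusion in both site-specific searches is an error.** An effusion of unstated site is not evidence of both sites, but counting it in both is a defensible sensitive definition. The rows are not stated to be mutually exclusive, and no sum across them is planned.
- **That Swelling Face events are known to occur, or that 33.8% edema and 33.9% pleural effusion rest on these searches.** The exclusion list does not say that each term was observed, and Protocol Section 3.5 does not say how its percentages were derived.
- **That the cutaneous list permits a data-driven definition.** The SAP says "The observed TEAEs under this SOC will be medically adjudicated to maintain a list of PTs that are not medically relevant" and gives no freeze date. But the SAP is to be final before unblinding (Section 3.0), and the sponsor stays blinded (Protocol Section 5.5.5.1). At most this calls for a date on the list.

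**Conclusion.** The point holds as two specific gaps in Table 3. Swelling Face falls into no listed AESI search although its neighbours are in Edema. The protocol's serosal-effusion group has neither an ascites term nor a row of its own. Subjects with only those terms drop out of the grouped incidence and the time-to-onset analysis, and the other planned tables do not restore either.

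The effect on reported rates is unknown, because the documents give no counts. It is 0.27 percentage points per affected subject, assuming about 370 treated subjects per arm. If no subject has these terms alone, the rates do not change. Primary efficacy, type I error and between-arm inference are untouched. This is a correction to the safety summaries, worth making because it is specific and nearly free.

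**What to change.** Amend SAP Table 3 before unblinding:

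1. Add 10042682 Swelling Face to the Edema search.
2. Add one AESI row for any serosal effusion: the pleural terms, the pericardial terms, ascites and unspecified Effusion, with each subject counted once and onset taken at the first such event.
3. Keep 10063045 Effusion in both site-specific searches if the sensitive definition is wanted, with a footnote that it counts in both. The combined row then gives the count without duplication.

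The cost is a small edit to one table, one extra row in the incidence and onset outputs, and possibly a slightly higher edema rate. No new data are needed.
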